5.7.4 Medical History

Clinically significant medical history events for the five years preceding screening will be coded using the latest Medical Dictionary for Regulatory Activities (MedDRA) dictionary version. The version used will be indicated in the data summaries and listings. The number and percentage of subjects will be presented for ongoing conditions and previous conditions separately by system organ class (SOC), and preferred term (PT), where SOC and PT will be presented in decreasing frequency of the total number of subjects with medical history events. All events will be listed.

5.7.5 Previous Melanoma Treatment, Radiotherapy and Surgery

A summary table will present any previous melanoma treatments, including adjuvant (after surgery), neo-adjuvant (prior to surgery) and advanced disease treatments. Medications will be coded using the latest World Health Organization Drug dictionary (WHO Drug) version. The version used will be indicated in the data summary and listing. All treatments will be listed.

Previous radiotherapy will be categorically summarised including the number and percentage of subjects receiving radiotherapy and the radiotherapy location. All instances of radiotherapy will be listed.

Previous melanoma surgery will be coded using the latest MedDRA dictionary version. The version used will be indicated in the data summaries and listings. The number and percentage of subjects receiving surgery for melanoma will be presented by SOC and PT, where SOC and PT will be presented in decreasing frequency of the total number of subjects receiving surgical procedures. All events will be listed.

5.8 Prior and Concomitant Medications

Medications will be coded using the latest WHO Drug version. The version used will be indicated in the data summaries and listings.

Prior medications are defined as those that started and ended prior to the first administration of IMM-101. Medications that are ongoing at the first administration of IMM-101 or started after time of first administration will be deemed to be concomitant medications. If medication dates are incomplete and it is not clear whether the medication was concomitant, it will be assumed to be concomitant.

The number and percentage of subjects taking prior and separately concomitant medications will be summarised by medication class and standardised medication name, where medication class and standardised medication name will be presented in decreasing frequency of the total number of subjects with medications. In summary tables, subjects taking multiple medications in the same medication class or having the same standardised medication recorded multiple times in the study will be counted only once for that specific medication class and standardised medication name.

Medication data will be listed, where concomitant medications will be flagged.

5.9 Concomitant Surgical Procedures

Concomitant surgical procedures will be coded using the latest MedDRA dictionary version. The version used will be indicated in the data summaries and listings. Procedures that occurred on or after the first administration of IMM-101 will be deemed to be concomitant procedures. If surgical procedure dates are incomplete and it is not clear whether the surgery was concomitant, it will be assumed to be concomitant. All surgeries performed prior to first administration of IMM-101 and not related to melanoma surgery will be included within the medical history summaries and listings. All surgeries performed prior to first administration of IMM-101 and related to melanoma surgery will be included within the previous melanoma related surgery summaries and listings.

The number and percentage of subjects receiving surgery will be presented by SOC and PT, where SOC and PT will be presented in decreasing frequency of the total number of subjects receiving surgical procedures. All events will be listed.

5.10 Post-Completion/Withdrawal Anti-Melanoma Treatment

Any anti-melanoma medications received after completion or withdrawal from IMM-101 will be listed. Medications will be coded using the latest WHO Drug version. The version used will be indicated in the listing.

5.11 Administration of IMM-101, Nivolumab and Ipilimumab

Administration details for each study treatment will be listed in full.

For IMM-101, this will include the date and time of administration, details of any delays, the arm chosen for injection, the dose administered and confirmation of the vital signs monitoring. If the dose was not administered, reasons for the missed dose will also be listed.

Nivolumab infusion information will include the date and time of administration, details of any delays, the regimen chosen and regimen modifications, the planned and actual dose with reasons for any differences between the two. If the dose was not administered, reasons for the missed dose will also be listed.

Ipilimumab infusion details will include the date and time of infusion, infusion number, delay details, the planned and actual dose with reasons for any differences between the two will be listed. The date and reason for treatment with ipilimumab will also be listed.

5.12 Exposure and Compliance

An exposure summary will include the time on study, the overall exposure of each of IMM-101, nivolumab and ipilimumab and the total dose exposure of nivolumab. The number of doses of IMM-101, and whether they were full or half doses will also be summarised.

The time on study will be calculated in months as (date of completion/withdrawal - date of first IMM-101 administration + 1)/30.4375.

Overall exposure to each of IMM-101, nivolumab and ipilimumab will be calculated in months as (date of last administration – date of first administration + 1)/30.4375.

Total nivolumab exposure will be calculated in mg across the duration of the subject's participation as the sum of the total dose administered at each nivolumab dosing visit for each subject.

Compliance will be summarised for IMM-101, nivolumab and ipilimumab separately for each visit.

For IMM-101, the number of subjects receiving treatment and whether these were full or half doses, the number of subjects not dosed, the reason for not dosing, the number of subjects with delayed dosing and the reasons for the delay will be summarised.

For nivolumab, the number of subjects receiving the infusion and the reasons if they did not receive the infusion, the number of subjects with delayed infusion and reasons for delayed infusion, the dosing regimen chosen and whether the regimen was modified will be summarised. The number of subjects who received less than, more than or exactly the planned dose will also be summarised.

For ipilimumab, the number of subjects receiving the infusion and the reasons why they received the infusion will be summarised. For each of the four infusions, the

number of subjects with delayed infusion and reasons for delayed infusion and the number of subjects who received less than, more than or exactly the planned dose will also be summarised.

5.13 EFFICACY EVALUATION

5.13.1 Primary Endpoint

The primary endpoint will be analysed using the ITT set and repeated for the PPS for Cohort A only.

Primary Analysis

The primary efficacy endpoint of the study is the ORR calculated from the BOR of subjects as assessed by RECIST 1.1.

The investigator response will be entered into the Response Assessment (RECIST 1.1) page of the electronic Case Report Form (eCRF) at each scan assessment to be used in the derivation of BOR.

A confirmed response will be used in the derivation of BOR. A confirmed response is defined as a response obtained from a scan repeated at least 4 weeks following a scan with designation of complete response (CR) or partial response (PR), as defined using Table 3 of RECIST 1.1. In addition, the following approaches will be taken:

- Where a confirmatory assessment is non-evaluable (NE) but the subsequent scan maintains the same response/progression, the response/progression will be considered confirmed (e.g. PR-NE-PR).
- Subjects without a confirmed response of CR or PR will have their next best response (stable disease (SD) or otherwise progressive disease (PD)) assigned as their BOR.
- Subjects without a BOR assessment, such as those with no post-baseline responses or only NE responses, will be assumed to have a BOR of PD using a worst-case approach.

For Cohort A, BOR is defined as the best confirmed response designation, recorded from the first post-baseline scan until and including the last scan on study for each subject.

For Cohort B, BOR is defined as the best confirmed response designation, recorded from the first post-baseline scan until and including the last scan on study for each subject for those receiving IMM-101 and nivolumab, or the last scan performed prior to treatment with ipilimumab. No scan performed once ipilimumab treatment commences will be included.

All scans within these periods, whether scheduled or unscheduled, will be evaluated for overall response.

ORR is calculated as the number of subjects with a BOR of confirmed CR or PR divided by the number of subjects in the analysis set. ORR is calculated for each cohort separately.

Summaries of BOR (best confirmed overall response designation)

The BOR will be summarised for each cohort. The ORR and accompanying exact binomial 95% confidence intervals (CI) will also be presented.

Listings of lesions assessments and BOR

Listings of the baseline and follow-up target lesions will be provided. These listings will be presented for both assessment using RECIST 1.1 and repeated for assessment using irRC. The response assessment for both RECIST 1.1 and irRC will also be listed. Listings of non-target lesions at baseline and follow-up will be presented. New lesions found after baseline will be listed and the assessments of these previously reported new lesions will also be listed.

A BOR listing will present the responses derived using RECIST 1.1 including confirmed responses only, unconfirmed responses, all responses (confirmed or unconfirmed) up until progression, confirmed responses at interim assessment, and all responses (confirmed or unconfirmed) including those after a treatment change in Cohort B. The BOR derived using irRC will also be presented.

Sensitivity Analysis

Two sensitivity analyses will be performed for comparability with published data:

1. The summary table will be repeated with BOR assessed using confirmed or unconfirmed responses.
2. The summary table will be repeated with BOR assessed using confirmed or unconfirmed responses up until disease progression (i.e. excluding any PR and CR responses following a PD response).

Unconfirmed responses do not need to follow Table 3 of RECIST 1.1. Instead, the BOR is defined as the best overall response during the defined period and does not need to be confirmed at a subsequent timepoint, hence overall responses whether confirmed or not are assessed in the evaluation of BOR.

Exploratory Analysis

Further summaries by subgroup will be provided where BOR is assessed using unconfirmed responses.

The summary table described above will be repeated for each of the following subgroups:

- PD-L1 status at screening (positive/negative or indeterminate) for Cohort A only.
- M staging at screening (M1c and M1d/M0, M1a and M1b) for Cohort A only.
- BRAF status at screening (wild type/mutant) for Cohort A only.
- LDH at baseline (\leq upper limit of normal/ $>$ upper limit of normal) for Cohort A and B.

The criteria for presentation of these outputs are described in Section 5.2.8.

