# 8.5.3.9 Missing Assessments and Not Evaluable Designation

When no imaging/measurement is done at all at a particular time point, the subject is not evaluable (NE) at that time point. If only a subset of lesion measurements are made at an assessment, the case is also considered NE at that time point, unless a convincing argument can be made that the contribution of the individual missing lesion(s) would not have changed the assigned time-point response (for example if the criteria for PD are reached by the lesions that have been assessed).

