5.13.2 Secondary Endpoints

5.13.2.1 PFS Assessed by RECIST 1.1 for Cohorts A and B

PFS will be analysed using the ITT set and analysis will be repeated for the PPS for Cohort A only.

PFS is defined in months as the time between Visit 1 and the first confirmation of progression using RECIST 1.1, or death from any cause (whichever occurs first) (date

of first progression or death – date of Visit 1 + 1). Progression is determined by the investigator using the CT or MRI scan (scheduled or unscheduled) or death due to any cause. Subjects who die without reported progression will be considered to have progressed on the date of their death.

The following censoring rules will apply:

- Subjects who did not progress or die will be right censored on the date of their last evaluable tumour assessment.
- Subjects who did not have any on-study tumour assessments (scans) and did not die will be right censored on their date of first post-Screening visit. Note that this definition is consistent with that used for [Checkmate 067](#)².
- Subjects who remain on study following radiotherapy or other prohibited treatment will be censored at their last scan assessment prior to the intervention therapy.
- Subjects in Cohort B who change therapy to IMM-101 + ipilimumab without documented progression by RECIST 1.1 will be censored at the date of their last evaluable tumour assessment prior to this change in therapy.

Summaries of PFS

Descriptive statistics will be presented for PFS. The number and percentage of subjects that are censored will be summarised, along with KM estimates for the 25th, 50th and 75th percentiles of PFS and corresponding 95% CIs. PFS will also be presented graphically using a KM plot. The proportion of subjects who have not progressed or died at three monthly intervals will also be presented.

A time to event listing will present the milestones required for calculation of each time to event efficacy parameter.

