5.13.3.2 Duration of Response Assessed by RECIST 1.1 for Cohorts A and B

Duration of response will be analysed using the ITT set and only subjects who have a documented response of CR or PR will be included.

Duration of response is calculated as the time in months from the date of first documented response of CR or PR per RECIST 1.1 until the date of documented PD per RECIST 1.1 or until the date of death due to any cause (date of death or PD – date of documented response + 1). All scans are considered, whether scheduled or unscheduled, in the determination of response and confirmed responses are not required.

Subjects who neither progress nor die will be right censored on the date of their last tumour assessment. For Cohort B subjects who change treatment to IMM-101 and ipilimumab, only responses evaluated until the point of this change in therapy are included.

Summaries of duration of response

Descriptive statistics will be presented for duration of response. The number and percentage of subjects that are censored will be summarised, along with KM estimates for the 25th, 50th and 75th percentiles for the duration of response and corresponding

95% CIs. The proportion of subjects who have not progressed or died following a complete or partial response at three monthly intervals will also be presented.

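### The SAP labels patients with no evaluable post-baseline scan as progressive disease, so the PD row of the best overall response tables mixes missing data with documented progression

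*SAP*

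**What the plan says.** SAP 5.13.1 tabulates BOR by category beside ORR ("The BOR will be summarised for each cohort") and has two fallback rules.

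- **Rule 1, no usable assessment.** Subjects with no post-baseline response, or only NE responses, "will be assumed to have a BOR of PD using a worst-case approach". SAP 5.13.3.1 (irRC) and 5.13.3.5 (Cohort B including ipilimumab) impute PD in the same way. SAP 4.2 refers to 5.13.1 for the BOR derivation at the interim.
- **Rule 2, unconfirmed response.** Subjects without a confirmed CR or PR "will have their next best response (stable disease (SD) or otherwise progressive disease (PD)) assigned as their BOR". Confirmation itself is "as defined using Table 3 of RECIST 1.1", and neither document reproduces that table.

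Other sections treat the same patients as follows.

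- Protocol 8.5.3.9 designates a time point without imaging NE. Protocol 10.1.2 lists only CR, PR, SD and PD for BOR and sets a 9-week minimum for SD.
- For PFS, SAP 5.13.2.1 says that subjects who "did not have any on-study tumour assessments (scans) and did not die will be right censored on their date of first post-Screening visit". Others without progression or death are censored at the last evaluable scan, and death without progression is an event.
- SAP 5.13.3.2 and 5.13.3.3 admit only patients with a documented CR or PR to duration of response and time to response. For both, "confirmed responses are not required".

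**The concern.** PD is an observation, whereas a missing or unreadable scan is the absence of one. Calling the imputation worst-case suggests that it protects the primary analysis, but the ORR needs no protection. "ORR is calculated as the number of subjects with a BOR of confirmed CR or PR divided by" the number in the analysis set, so an unscanned patient is a non-responder under either label. The only thing that the rule changes is the PD row.

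A reader will take that row as the share of patients whose best outcome was progression, and SAP 2.1 intends the results to be compared with published nivolumab data. A living, never-scanned patient would appear as PD in the primary table and as censored in PFS.

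Cohort B has a route to this built into the design. Protocol 5.1 and 7.5 allow a switch to ipilimumab for clinical progression without RECIST progression, and SAP 5.13.1 ignores scans after the switch. A patient who switches before an evaluable scan is PD by imputation in the primary table.

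**Working it through.** The plan gives no figure of its own here. The check applies the SAP rules, read literally, to the same scan histories and then sizes the effect.

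**Inputs.** Planned N is 18 (Cohort A) and 8 (Cohort B), from SAP Section 3. Interim N for ORR is 11 and 5, from SAP Section 4. The rules are those described above.

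**Step 1: one patient, three analyses.**

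| Scan history before any switch | BOR (5.13.1) | PFS (5.13.2.1) | Duration of / time to response | Conflict |
|---|---|---|---|---|
| No scan, alive | PD, rule 1 | Censored at Visit 1 | Not included | PFS only |
| No scan, died | PD, rule 1 | Event at death | Not included | None |
| Only NE scans, alive | PD, rule 1 | Censored; no date rule fits exactly | Not included | PFS only |
| CR or PR, no later evaluable scan, alive | PD, rule 2 read literally | Censored at that scan | Responder; duration censored | PFS and both response-time analyses |
| PR, then PD | PD, rule 2 read literally | Event | Responder; duration event | None |
| SD, then unconfirmed PR, alive | SD | Censored at last evaluable scan | Responder | No PD label |

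Rule 1 can disagree with PFS but never with duration of response, because its patients are not in that analysis. Only the fourth history disagrees with both.

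**Step 2: size per patient.** Shift in the PD row = 1/N.

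- Final analysis: 1/18 = 5.6 points (Cohort A); 1/8 = 12.5 points (Cohort B).
- Interim: 1/11 = 9.1 points (Cohort A); 1/5 = 20.0 points (Cohort B).
- Two patients at the final analysis: 2/18 = 11.1 points; 2/8 = 25.0 points.

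**Step 3: ORR.** Relabelling PD as NE changes neither numerator nor denominator. With assumed counts, 8/18 = 44.4% (exact 95% CI 21.5 to 69.2%) and 1/8 = 12.5% (0.3 to 52.7%), the same before and after.

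**Step 4: which tables are affected.** Rule 1 applies in 5.13.1, 5.13.3.1 and 5.13.3.5. Rule 2 applies in 5.13.1 only, because the other two use unconfirmed responses, so a lone PR appears there as PR.

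**Step 5: the SD minimum.** SAP 5.13.1 does not restate the 9 weeks. Protocol 10.1.2 counts them from Screening, whereas Protocol 10.6 and SAP 5.13.3.4 count from the first IMM-101 dose. Cohort A's first scheduled scan, at Week 12, passes either way. For Cohort B's Week 6 scan the origin matters: with a baseline scan 21 days before dosing, 6 + 3 = 9 weeks from Screening, but only 6 from first dose.

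**The case against.** The case for leaving the text alone has several sound parts.

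- **The rule is prespecified and permitted.** Protocol 11.5 leaves missing-data rules to the SAP. NE in the protocol is a time-point designation, and Protocol 10.1.2 gives BOR no NE category. This stands. It makes the rule allowable, but the PD row still does not mean documented progression.
- **Imputation and censoring are different conventions.** Censoring at Visit 1 means status unknown with no follow-up; it does not declare the patient progression-free. That is fair, and it supports NE as the label in the BOR table too.
- **The primary estimate does not move.** ORR and its interval are unchanged, and no endpoint uses the PD row. This limits the weight of the point.
- **Other outputs help.** Listings show individual responses. The two sensitivity tables show a lone unconfirmed PR as PR. Lack of a post-baseline measurable scan is a possible major deviation (SAP 5.6), so such patients may leave the Cohort A per-protocol repeat. None of this removes the imputed PD from the ITT summary tables.
- **Rule 2 may not work as it reads.** It sits beside RECIST Table 3, which cannot be consulted here. Patients who stop for reasons other than progression, with no further treatment planned, should continue scans until progression (Protocol 5.1, 5.3, 6.3, 6.4). Stopping for toxicity therefore does not by itself produce a lone PR. This stands, and the pattern is narrow.

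A reader might go further and infer that Rule 1 makes the response table contradict duration of response, or that unconfirmed shrinkage inflates PD in the irRC and post-ipilimumab tables. The documents support neither. Duration of response excludes Rule 1 patients, and those two tables count unconfirmed responses. Nor do unscanned deaths or PR followed by PD conflict with PFS, since both are PFS events. Counting an unconfirmed responder in duration of response but not in the confirmed ORR is the protocol's own design (10.1.2 to 10.1.4).

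**Conclusion.** The concern holds for Rule 1. As written, the BOR tables in SAP 5.13.1, 5.13.3.1 and 5.13.3.5 report progression that nobody documented, and a living patient with no scan or only NE scans is PD in the BOR table and censored in PFS. The shift is 5.6 points per patient in Cohort A and 12.5 in Cohort B at planned enrolment, or 9.1 and 20.0 at the interim. These are per-patient figures, because the documents give no expected frequency. If every patient has an evaluable post-baseline scan, Rule 1 has no effect.

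Rule 2 is a lesser point of wording, confined to 5.13.1. It rests on a literal reading, on a patient who is alive with a single evaluable scan, and on how the bullet interacts with RECIST Table 3. Whatever that table says, the SAP should not leave this outcome to interpretation.

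Neither rule changes ORR or its confidence interval. The point is worth correcting because the tables are small and meant for external comparison, not because the primary result is at risk.

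**What to change.** 1. In SAP 5.13.1, 5.13.3.1 and 5.13.3.5, keep patients with no evaluable post-baseline scan in the denominator as non-responders, report them in a separate NE row, and reserve PD for documented progression. Code NE as a category rather than as missing: SAP 5.1 bases most percentages on non-missing observations and does not list efficacy among the exceptions.
2. In SAP 5.13.1, state that where there is no confirmed response and no qualifying SD scan, an unconfirmed CR or PR at or after the protocol's 9-week SD minimum is classed as SD. Otherwise the BOR is PD only if PD was documented, and NE if it was not. Name the date from which the 9 weeks run, and say how the bullet relates to RECIST Table 3. This would also class a Week 12 PR followed by PD as SD.
3. Record the added NE category in SAP Section 6, because Protocol 10.1.2 lists only four BOR categories.

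The cost is a few sentences and one extra row in the table shells. No new data are needed, and ORR and its interval stay as planned.

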## 6. SELECTION AND WITHDRAWAL OF PATIENTS

## 6.1 PATIENT INCLUSION CRITERIA

A patient must meet all of the following criteria to be eligible to participate in this study:

- 1. Patient must have a histologically-confirmed diagnosis of advanced (unresectable Stage III) or metastatic (Stage IV) melanoma excluding uveal/ocular melanoma. Patients with unknown primary melanoma are eligible
- 2. Patient has at least one measurable lesion by CT or MRI, according to RECIST 1.1.
- 3. Patient must have known BRAF V600 mutation status or consent to BRAF V600 mutation testing during the Screening Period.

- 4. Patients who have had prior radiotherapy must have been completed this at least 2 weeks prior to study drug administration (Week 0, Visit 1). Prior adjuvant or neoadjuvant melanoma therapy is permitted if it was completed at least 6 weeks prior to enrolment (Week 0, Visit 1), and all related adverse events have resolved or stabilised.
- 5. Patient is considered suitable for treatment with nivolumab.
- 6. Patient provides signed informed consent for participation in the study.
- 7. Patient has an Eastern Cooperative Oncology Group (ECOG)/World Health Organisation (WHO) Performance Status of ≤1 at Day 0.
- 8. Patient has Screening laboratory values meeting the following criteria. These should be obtained within 14 days prior to first dose on study:
  - Haemoglobin (Hb)  $\geq$ 9.0g/dL, absolute neutrophil count  $\geq$ 1.5 x 10^9/L, platelets  $\geq$ 100 x 10^9/L and White Blood Cells (WBC)  $\geq$  2.0 x 10^9/L (blood transfusion to achieve these levels are not permitted within 2 weeks of this assessment)
  - Total bilirubin ≤1.5 x upper limit of normal (ULN), excluding cases where elevated bilirubin can be attributed to Gilbert's Syndrome
  - Aspartate transaminase (AST; serum glutamic oxaloacetic transaminase [SGOT])
    and alanine transaminase (ALT; serum glutamate pyruvate transaminase [SGPT])
    each ≤2.5 x ULN or ≤5 x ULN in presence of liver metastases
  - Creatinine ≤1.5 x ULN
  - Serum albumin ≥30g/L
- 9. Patient is aged  $\geq$ 18 years.

For cohort A, the following inclusion criteria must also be met for a patient to be eligible to participate in this study:

- 1. Patient is treatment-naive (i.e., no prior systemic anticancer therapy for unresectable or metastatic melanoma).

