#### 6.5 CONCOMITANT MEDICATIONS

#### **6.5.1** Prohibited Medications

Medications or vaccinations specifically prohibited in the exclusion criteria are not allowed during this study. If there is a clinical indication for a medication or vaccination specifically prohibited during this study, discontinuation from study therapy may be required, with the decision to continue the patient on the study being made by the mutual agreement of the Investigator, the Sponsor and the patient.

Patients are prohibited from receiving the following therapies during the Screening and Treatment Phase of this study:

- Antineoplastic systemic chemotherapy or biological therapy
- Immunosuppressive agents, except for acute treatment of potential immune-related AEs during the study
- Systemic corticosteroids >10 mg daily prednisolone equivalent, unless for acute treatment of potential immune-related AEs during the study. Systemic corticosteroids ≤10 mg daily prednisolone equivalent for more than 2 weeks are also prohibited
- Other investigational agents
- Radiation therapy apart from to a symptomatic solitary lesion which may be allowed
  at the discretion of the Investigator and after consultation with the Sponsor. Such
  therapy is only allowable after the first scheduled tumour assessment on study, unless
  otherwise agreed with the Sponsor
- Live vaccines within 30 days prior to the first dose of study therapy and while participating in study. Examples of live vaccines include, but are not limited to: measles, mumps, rubella, chicken pox, yellow fever, seasonal flu, H1N1 flu, rabies, BCG, and typhoid vaccine

Page 40 of 98

In addition, cytokines (e.g., Interferon alpha [IFN- $\alpha$ ]), monoclonal antibodies, anti-tumour vaccines, and biological response modifiers should be used with caution when given concomitantly with IMM-101.

Any prior and concomitant therapy/medications taken up to 30 days before the first dose of study medication will be recorded in the patient's eCRF at Screening.

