Patients in cohort B who fail to respond to treatment with IMM-101 + nivolumab i.e., they have either documented progression by RECIST 1.1, or clinical progression (but without meeting the RECIST 1.1 rules for progressive disease), and, in both cases have no prior recorded response, have the option to change treatment on study to ipilimumab + IMM-101 if the investigator considers this in the patient's best interest and the patient has not previously received ipilimumab off study (monotherapy or in combination). Any patients who discontinue study treatment for reasons other than progression and for whom no further treatment is deemed appropriate or desired, should remain on study and have scheduled scans until documented progression.

At baseline, tumour lesions/lymph nodes will be categorised as measurable or non-measurable as follows:

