## **Lesions with prior local treatment:**

• Tumour lesions situated in a previously irradiated area, or in an area subjected to other loco-regional therapy, are usually not considered measurable unless there has been demonstrated progression in the lesion.

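### On-study radiotherapy ends follow-up for PFS but not for best overall response, so shrinkage of an irradiated target lesion can count in the primary ORR, and no planned table reliably isolates it

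*SAP*

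**What the plan says.** **Primary response.** SAP 5.13.1: "For Cohort A, BOR is defined as the best confirmed response designation, recorded from the first post-baseline scan until and including the last scan". Every scan in that window is evaluated, scheduled or not. Cohort B has the same window with one limit: "No scan performed once ipilimumab treatment commences will be included". Protocol 10.1.2 and 11.1.5 also run to the last imaging on study. Protocol 5.2.1 stops at the end of study treatment.

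**PFS.** SAP 5.13.2.1: "Subjects who remain on study following radiotherapy or other prohibited treatment will be censored at their last scan assessment prior to the intervention therapy". Protocol 5.2.2 and 10.2 contain no such rule, and SAP section 6 does not list it as a change.

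**Radiotherapy on study.** Protocol 6.5.1 includes among the prohibited therapies "Radiation therapy apart from to a symptomatic solitary lesion which may be allowed" at the Investigator's discretion after consulting the Sponsor, normally only once the first scheduled tumour assessment has been done.

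**Lesions.** Eligibility (Protocol 6.1) requires: "Patient has at least one measurable lesion by CT or MRI, according to RECIST 1.1". On earlier local treatment, Protocol 8.5.1.3 says: "Tumour lesions situated in a previously irradiated area, or in an area subjected to other loco-regional therapy, are usually not considered measurable" unless the lesion has since progressed. That text falls under the introduction "At baseline, tumour lesions/lymph nodes will be categorised as measurable or non-measurable as follows".

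**Sensitivity analyses.** SAP 5.13.1 plans two. The first also accepts unconfirmed responses. The second reads: "The summary table will be repeated with BOR assessed using confirmed or unconfirmed responses up until disease progression".

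**The concern.** The SAP treats a switch to ipilimumab consistently: later scans are dropped for PFS (where progression was not already documented) and for response. It treats radiotherapy as an interfering therapy for PFS only. The same patient could therefore be censored for PFS because of radiotherapy and counted as a confirmed responder because of it.

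The ORR is one of the two primary endpoints. Protocol section 4 says efficacy will be compared with published nivolumab data, and Protocol 3.4 cites a 44% response rate in treatment-naive patients. In cohorts of 18 and 8, one response due to local therapy visibly moves the headline figure, and a reader of the planned tables could not tell that it had.

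**Working it through.** The plan gives no figure that depends on this point: there is no formal sample size calculation, test or decision rule. The check is a comparison of rules, followed by arithmetic on possible size.

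**1. Does any response window exclude the scans?** SAP 5.13.1 and Protocol 10.1.2 and 11.1.5 do not. The narrower window in Protocol 5.2.1 does not help, because permitted radiotherapy does not end study treatment.

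**2. Does any lesion rule exclude the lesion?**
- Protocol 8.5.1.3 (lesions with prior local treatment) concerns measurability, which is assigned at baseline.
- Protocol 8.5.2 allows target lesions to be reassigned later only to correct a genuine error.
- Protocol 8.5.3.3 requires lesions recorded at baseline to be measured at each later evaluation.
- Protocol 8.5.3.9 assigns a not-evaluable result only when imaging or lesion measurements are missing.
- Protocol 6.5.4 covers surgery (a PR stays a PR after the remaining disease is resected) and has no counterpart for radiotherapy.

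Read literally, a target lesion irradiated on study stays in the sum.

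**3. When would that produce a PR?** Protocol 8.5.3.1 needs a fall of at least 30% from the baseline sum. With other target lesions unchanged, the condition is (lesion's share of baseline sum) × (its shrinkage) ≥ 0.30, so minimum share = 0.30 / shrinkage:
- lesion disappears: 0.30 / 1.00 = 30% of the sum
- shrinks 60%: 0.30 / 0.60 = 50%
- shrinks 50%: 0.30 / 0.50 = 60%
- shrinks 30%: 0.30 / 0.30 = 100%, a sole target lesion

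For example, if a 60 mm lesion in a 90 mm sum halves, (30 + 30)/90 − 1 = −33.3%, a PR. If a 50 mm lesion in a 100 mm sum halves, (25 + 50)/100 − 1 = −25%, which is SD. The PR must also be confirmed at least 4 weeks later, with no new lesion or non-target progression.

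**4. Size per patient** (exact Clopper-Pearson 95% intervals; response counts are illustrative)
- Cohort A: 1/18 = 5.6 points. For example, 8/18 = 44.4% (21.5 to 69.2) becomes 9/18 = 50.0% (26.0 to 74.0).
- Cohort B: 1/8 = 12.5 points. For example, 1/8 = 12.5% (0.3 to 52.7) becomes 2/8 = 25.0% (3.2 to 65.1).
- Interim reviews of the first 11 and 5 subjects (SAP 4.2): 1/11 = 9.1 and 1/5 = 20.0 points.

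**5. Would a planned table show the ORR without the case?**
- Sensitivity analysis 1 widens the definition and keeps it.
- Sensitivity analysis 2 removes it only if RECIST progression preceded the response. It also admits unconfirmed responses, so it changes two things at once.
- The Per-Protocol Set might remove it. SAP 5.6 names prohibited medication thought likely to affect efficacy as a possible major deviation. That is a case-by-case judgement, radiotherapy the protocol permits need not be a deviation, and SAP 5.3 restricts per-protocol outputs to Cohort A.

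**The case against.** The strongest reply is that a response window and a PFS censoring rule need not match. SAP 5.13.1 follows the protocol's primary definition, and nothing is tested or decided on the ORR. A false response also needs several things together: a symptomatic solitary lesion, Sponsor consultation, no response already confirmed, an irradiated lesion that dominates the target sum, no progression elsewhere, and confirmation. With 26 planned patients, the lesion, response and time-to-event listings would let a careful reader trace the case. Reading details are deferred to a Study Operations Manual that is not among the documents, and Protocol 5.3 lets a scan be called inevaluable with a reason.

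Most of this stands. It limits the likely size and rules out calling the primary definition an error. It does not close the gap: the SAP neither states nor cites a reading rule for lesions irradiated on study, and tracing a case in listings is not a prespecified estimate.

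A reader might infer that the PFS trigger should simply be copied into the primary ORR. The documents do not support that. The trigger extends to any other prohibited treatment, and Protocol 6.5.1 prohibits live vaccines (seasonal flu is a listed example) and low-dose systemic corticosteroids beyond 2 weeks. Copied over, it could erase genuine later responses at the same 5.6 or 12.5 points each. Duration of response and time to response (SAP 5.13.3.2 and 5.13.3.3) would also be left on a different window.

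**Conclusion.** The mismatch is real, and closing it is a worthwhile, inexpensive improvement. Followed as written, the plan can score radiotherapy shrinkage as a confirmed response in the primary ORR, worth 5.6 points per patient in Cohort A and 12.5 in Cohort B at the planned sizes. This assumes that no rule in the unsupplied operations manual intervenes and that readers keep the irradiated lesion in the sum.

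Two stronger readings go too far. One is that the ORR will be inflated: the documents give no expected number of irradiated patients, it may be zero, and the example intervals overlap widely. The other is that no planned table could show the ORR without the case. The Cohort A per-protocol table might, at the data review meeting's discretion, and sensitivity analysis 2 does so where progression came first. The supportable statement is that no planned table does so reliably, and that none does so in Cohort B unless progression came first.

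**What to change.** Keep the primary ORR as the protocol defines it. Before database lock, add a third sensitivity analysis to SAP 5.13.1, for both cohorts on the ITT set:
- Use confirmed responses, as in the primary analysis.
- Do not count scans after on-study tumour-directed radiotherapy or non-protocol systemic anticancer therapy toward BOR.
- Keep responses confirmed before the intervention, and keep the subject in the denominator. The existing SAP 5.13.1 rules for unconfirmed or absent responses then apply.
- Do not use the wider trigger of any other prohibited treatment.
- State that protocol ipilimumab is not a trigger; the Cohort B primary window already ends there.

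The cost is one extra table. No new data are needed: Appendix 1 of the protocol records radiotherapy at visits, Protocol 6.5.3 records procedure dates, and the PFS rule already needs the intervention date. The irradiated lesion does not have to be identified. The downside, confined to this table, is that two kinds of response are not counted: one seen but not yet confirmed before radiotherapy, and a genuine one arising after radiotherapy to a non-target lesion.
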